RECIST v1.1 criteria do not mention including or excluding lesions that are being biopsied or injected. However, for the purposes of this protocol, the injected and biopsied lesions are to be captured as non-target lesions only (Phase I only), as follows:

- Injected and biopsied lesion = non-target lesion #1
- Non-injected and biopsied lesion = non-target lesion #2 (if applicable)

See Schedule of Assessments and Study Activities (Table 1 and Table 2) for details.

3.1.1 **Phase I – Dose Escalation Plan**

The Phase I dose escalation is illustrated in Figure 8 for monotherapy and Figure 9 and Figure 10

for combination therapy.

Phase I Dose Escalation – Monotherapy:

- Each dose escalation cohort will initially recruit at least 3 patients in a standard 3+3 design. To proactively ensure at least 3 patients are considered evaluable, a fourth patient may be enrolled and treated in addition to the initial 3 patients in each cohort (the fourth patient may only be enrolled if they are identified at the time the third patient slot is being filled).
- Dose escalation design in which administered dose levels will be escalated stepwise in successive cohorts of 3 to 6 (NOTE: 7 if fourth slot is filled and a single DLT is identified among the first 4 patients) patients per dose group until the RP2D or MTD level is identified.
- The first patient enrolled in each dose level must complete the first two weeks of Cycle 1 prior to enrolling the second and third (fourth when applicable) patients.
- Dose levels to be evaluated include (although not necessarily limited to) 100 µg (representing 1/60th of the pre-clinical HNSTD dose), 200 µg, 400 µg, 800 µg, and 1,200 µg.
- IMSA101 will initially be administered by intratumoral injections on Day 1 of Weeks 1, 2, and 3 for Cycle 1 (i.e., weekly dosing 3 out of 4 weeks), and on Day 1 of Weeks 1 and 3 (i.e., bi-weekly dosing) for all cycles thereafter.
- No dose escalation decisions will be made until all patients in a dose level complete the first 28 days of treatment. NOTE: this includes a fourth additional patient when applicable. Dose-escalation/de-escalation decisions will be based on the occurrence of DLTs during Cycle 1 of the evaluated dose level and the recommendation of the Cohort Review Committee (CRC).
- If no DLTs are observed among the initial 3 (4 when applicable) patients of an evaluated dose level, the dose will be escalated for the following 3 patients.

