3.4 BLINDING AND RANDOMIZATION

This is an open-label and non-randomized study; no blinding and randomization will be conducted.

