4.2 INCLUSION CRITERIA

Patients meeting all of the following criteria will be considered for enrollment into the study.

Phase I combination only:

- 1. Eligible patients will meet one of the following criteria:
 - Have radiographically-confirmed RECIST stable disease through ≥ 2 consecutive cycles of an approved PD-1 or PD-L1 targeted ICI administered as monotherapy
 - Be clinically stable following a first (unconfirmed) follow-up radiographic scan demonstrating progression of disease on ICI monotherapy
 - Have progression through prior ICI therapy administered either as mono or combination therapy
 - Have received no prior ICI therapy but otherwise be ineligible for all available standards of care
- 2. Have experienced no prior Grade \geq 3 CTCAE adverse events on ICI therapy that were considered by the investigator to be at least possibly ICI drug-related.

All patients (unless otherwise indicated):

- 1. Signed informed consent and mental capability to understand the informed consent
- 2. Male or female patients \geq 18 years of age
- 3. Histologically or cytologically documented locally advanced or metastatic solid tumor malignancies refractory to or otherwise ineligible for treatment with standard-of-care agents/regimens, including but not limited to:
 - Malignant melanoma
 - Hormone receptor negative breast cancer
 - Gastro-esophageal cancer
 - Non-small cell lung cancer

- Head and neck cancer
- Hepatoma
- Renal cell carcinoma
- 4. Eastern Cooperative Oncology Group (ECOG) performance status of ≤ 1 (Appendix 13.1)
- 5. Evaluable or measurable disease as follows:
 - 2 or 3 RECIST evaluable lesions: one that is suitable for injection and biopsied; an optional non-injected second lesion that will be biopsied for abscopal effect (only 1 patient per cohort required to have non-injected lesion biopsied; optional for all other patients in that cohort); and one measurable lesion that will be followed for response only.
 - Injectable tumors shall be accessed by intralesional (cutaneous) or percutaneous injection only, including those lesions that are visible, palpable, or detectable by standard radiographic or ultrasound methods. Neither surgical procedures nor endoscopically-guided injections including those to endobronchial, endoluminal, or endosinusoidal spaces shall be allowed. While no anatomic locations are required or disallowed, lesions selected for intratumoral injection must, in the opinion of the investigator:

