6.9 TUMOR ASSESSMENTS

All known tumor sites will be documented at screening and re-assessed at each subsequent time point for tumor evaluation, using a single and consistent methodology throughout all evaluations. Assessments may include the following:

- Screening (if a recent scan within the past month is not available in the medical records) and subsequent tumor assessments must include CT scans (with IV contrast unless contraindicated and oral contrast as appropriate per institutional standards) or MRI of the chest, abdomen, and pelvis (or other appropriate assessment). Photographic assessments of skin lesions will be performed through a photography vendor as detailed in a separate photography manual. At screening, photography assessment can be performed within 30 days prior to Day 1.
- If a CT scan is performed in a positron emission tomography/CT scanner, the CT acquisition must be consistent with the standards for a full-contrast CT scan.
- Brain imaging (by either MRI or contrast-enhanced CT) is required at screening for all patients displaying clinical signs of possible central nervous system involvement.
- Further investigations such as bone scans should be performed if there is any clinical suspicion of disease at any site that may not be observed using the methods above.

- The same radiographic procedures used to assess disease sites at screening should be used throughout the study (e.g., the same contract protocol for CT scans). Assessments should be performed by the same evaluator if possible to ensure internal consistency across visits.
- All findings will be assessed for response according to RECIST v1.1 criteria as defined in (Appendix 13.2) and according to the Schedule of Assessments and Study Activities (Table 1 and Table 2).

RECIST v1.1 criteria do not mention including or excluding lesions that are being biopsied or injected. However, for the purposes of this protocol, the injected and biopsied lesions are to be captured as non-target lesions only (Phase I only), as follows:

- Injected and biopsied lesion = non-target lesion #1
- Non-injected and biopsied lesion = non-target lesion #2 (if applicable)
- In certain circumstances a patient experiencing RECIST progression of disease may be allowed to continue therapy on study where there is agreement between the investigator and sponsor that the patient is deriving clinical benefit.

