13.2 RECIST GUIDELINE (VERSION 1.1)

All findings will be assessed for response according to RECIST v1.1 criteria (Eisenhauer, 2009) at the end (\leq 7 days) of every even numbered cycle (Cycle 2, Cycle 4, etc.), and EOT. Refer to Section 6.9 for details.

RECIST v1.1 criteria do not mention including or excluding lesions that are being biopsied or injected. However, for the purposes of this protocol, the injected and biopsied lesions are to be captured as non-target lesions only (Phase I only), as follows:

- Injected and biopsied lesion = non-target lesion #1
- Non-injected and biopsied lesion = non-target lesion #2 (if applicable)

All patients will have their BEST RESPONSE on study classified as outlined below:

Complete Response (CR)

Disappearance of all target lesions. Any pathological lymph nodes (whether target or non-target) must have reduction in the short axis to < 10mm.

Partial Response (PR)

At least a 30% decrease in the sum of diameters of target lesions, taking as reference the baseline sum LD.

Stable Disease (SD)

Steady state of disease. Neither sufficient shrinkage to qualify for PR nor sufficient increase to qualify for PD.

Progressive Disease

At least a 20% increase in the sum of diameters of measured lesions taking as references the smallest sum of diameters recorded since the treatment started. In addition to the relative increase of 20%, the sum must also demonstrate an absolute increase of at least 5 mm. Appearance of one or more new lesions will also constitute progressive disease.

Response Duration

Response duration will be measured from the time measurement criteria for CR/PR (whichever is first recorded) are first met until the first date that recurrent or progressive disease is objectively documented, taking as reference the smallest measurements recorded since the treatment started.

Stable Disease Duration

Stable disease duration will be measured from the time of start of therapy until the criteria for progression are met, taking as reference the smallest measurements recorded since the treatment started.

Target lesions	Non-Target lesions	New Lesions	Overall response
CR	CR	No	CR
CR	Non-CR-Non-PD	No	PR
CR	NE	No	PR
PR	Non-PD/ or not all evaluated	No	PR
SD	Non-PD/ or not all evaluated	No	SD
Not all evaluated	Non-PD	No	NE
PD	Any	Yes or No	PD
Any	PD	Yes or No	PD
Any	Any	Yes	PD

Evaluation of Best Overall Response – Patient with Target (+/- non-target) disease

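### Appendix 13.2 lets a CR or PR seen on one scan count as best response, although the next scheduled scan could confirm it

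*Combined protocol and SAP*

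**What the plan says.** **Response rule.** Appendix 13.2 opens its definitions with "All patients will have their BEST RESPONSE on study classified as outlined below". PR is then "At least a 30% decrease in the sum of diameters of target lesions, taking as reference the baseline sum LD", and CR is disappearance of the target lesions. Neither the definitions nor the overall-response tables ask for a repeat assessment.

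**Duration.** "Response duration will be measured from the time measurement criteria for CR/PR (whichever is first recorded) are first met". It ends at the first objective record of recurrence or progression.

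**Confirmation.** No section requires a response to be confirmed. The word unconfirmed is used only for prior progression on an ICI, in the Phase I combination eligibility (Sections 3.1.1 and 4.2).

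**Lesions.** Section 4.2 asks for two or three evaluable lesions, including "one measurable lesion that will be followed for response only". Sections 3.1 and 6.9 and Appendix 13.2 make injected and biopsied lesions non-target, in Phase I only.

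**Reading.** Section 3.4: "This is an open-label and non-randomized study; no blinding and randomization will be conducted". Section 6.9: "Assessments should be performed by the same evaluator if possible to ensure internal consistency across visits". No independent imaging review is described.

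**Schedule.** Cycles last 28 days (Section 10.2.2). Disease is assessed at the end of every even cycle and at EOT. Section 5.1.8 waives the EOT scan when one from the past month exists, and the visit after EOT (Section 5.1.9) records adverse events only.

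**Role of ORR.** The primary endpoint is MTD/RP2D (Section 2.4.1). ORR and DOR are listed as possible secondary efficacy endpoints (Section 2.4.3). Section 10.1.1 calls the Phase IIA statistics mainly descriptive and leaves the criteria for comparison with standard-of-care benchmarks to a later SAP.

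**The concern.** Best response takes the most favourable of several scans. A stable lesion therefore gets a new chance at each scan to be read as 30% smaller, and a later, larger reading does not cancel the PR. A falsely large baseline reading raises the chance at every later scan. Without a control arm, this inflation cannot be subtracted.

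DOR is exposed as well. Progression is judged against the smallest sum recorded, so one falsely low reading can create both a PR and, at the next scan, an apparent progression.

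What is at stake is the Phase IIA activity signal. Arms are small (20 patients in Section 3.1.2, about 20–25 in Section 4.1), so one or two false responses change how an arm looks. If a benchmark built on confirmed responses were later chosen, the comparison would also be between unlike quantities.

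**Working it through.** The plan states no response rate, benchmark, power or measurement error, so it has no figure of its own to reproduce. The check asks how often stable disease would be called PR under each rule.

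**Inputs from the protocol**
- PR threshold: follow-up sum ÷ baseline sum ≤ 0.70 (Appendix 13.2).
- Scan interval: 2 × 28 = 56 days, longer if the two-week cycle delay in Section 5.1.10 is used.
- Arm size: 20 (Section 3.1.2), so one response is 1/20 = 5 points of ORR.

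**Assumptions**
- Log-normal reading error with a coefficient of variation (CV) of 10–15% per lesion reading; 20% is shown as a stress case.
- True size unchanged, and one baseline reading shared by all comparisons.
- Three post-baseline scans, which is 6 × 28 = 168 days or 24 weeks on treatment.

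**Formula, one target lesion.** Let s = √ln(1 + CV²). Given a standardised baseline error u, the chance that one scan reads PR is p(u) = Φ((ln 0.70 + s·u)/s). Average over u ~ N(0,1):
- PR on any of three scans: 1 − (1 − p)³
- PR on two consecutive scans of three: 2p² − p³

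For a single post-baseline scan this reduces to Φ(ln 0.70/(s√2)). At CV 10%, s = 0.0998 and Φ(−2.53) = 0.6%. At CV 15%, s = 0.1492 and Φ(−1.69) = 4.5%.

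Results for three scans (the two-lesion case is simulated, with lesions of equal size):

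| Reading CV | One lesion: any scan | One lesion: two consecutive | Two lesions: any scan | Two lesions: two consecutive |
|---|---|---|---|---|
| 10% | 1.5% | 0.1% | 0.05% | <0.01% |
| 15% | 10.9% | 1.7% | 2.3% | 0.2% |
| 20% | 22.1% | 5.0% | 8.9% | 1.3% |

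Expected false PRs per 20 stable patients with one lesion:
- CV 10%: 0.3 on any scan, against 0.02 on two consecutive scans.
- CV 15%: 2.2 against about 0.35.

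**Effect on an arm of 20 (illustrative; the documents set no threshold).** Take a true ORR of 10%.
- A 5% false-PR rate among non-responders gives an expected ORR of 0.10 + 0.90 × 0.05 = 14.5%. A 10% rate gives 0.10 + 0.90 × 0.10 = 19%.
- The exact binomial chance of at least 4 responses in 20 rises from 13% to 33% and 54%.

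**Effect on DOR.** If a reading at 0.70 of baseline is followed by a return to baseline, the rise from the smallest sum is 1/0.70 − 1 = 43%, above the 20% progression threshold. The absolute rise is 0.30 × baseline, which meets the 5 mm condition once the baseline sum is at least 5/0.30 = 16.7 mm. The false response then enters DOR with a length of about 56 days.

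**The case against.** The strongest reply is that the matter is deferred rather than decided. The protocol cites RECIST v1.1 in general, a detailed SAP is to precede any analysis, and tumour types and futility rules are to come by amendment. It is fair to say that the protocol is silent on confirmation and does not expressly endorse unconfirmed responses. But Appendix 13.2 sets out a working rule that can be followed today, and that rule has no second look. A SAP not yet written does not change it.

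The size also depends on inputs that the documents do not give. That stands. With a second equal target lesion the single-scan rate at 15% error falls from 10.9% to 2.3%, and at 7% error with one lesion it is below 0.05%. Patients with fewer than three scans have lower rates.

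Four stronger readings are tempting, and the documents do not support them:
- **That response usually rests on one lesion.** One is the minimum; no distribution of lesion counts is given. The rule that keeps injected and biopsied lesions out of the target set applies to Phase I only, so an injected lesion may be a target in Phase IIA.
- **That reading error can only add responders.** It can also hide a true response near the threshold. The upward direction holds on balance in stable disease.
- **That scans are read locally.** This is not stated. The protocol only describes no independent review.
- **That ORR is the endpoint to be set against benchmarks.** Section 10.1.1 names no endpoint for that comparison.

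**Conclusion.** The point holds in a limited form. As written, a single-scan CR or PR counts as best response and starts the duration clock, and nothing elsewhere requires confirmation. Under 10–15% reading error, unchanged disease and three scans, false PRs fall from 1.5–10.9% to 0.1–1.7% with one target lesion, and from 0.05–2.3% to below 0.2% with two, when two consecutive scans are required. The lower end is negligible. The upper end, about two false responses per 20 stable patients, would matter to the Phase IIA signal.

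A reader might infer that the trial's main conclusion is at risk. It is not: MTD/RP2D rests on DLTs, and ORR is secondary and descriptive. This is an inexpensive improvement that should be settled before the SAP is final and any benchmark is chosen.

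**What to change.** In Appendix 13.2 and the SAP:

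1. Define the main ORR as CR or PR still present at the next scheduled even-cycle assessment.
2. Count patients without a confirming scan as non-responders in that analysis.
3. Report the unconfirmed ORR alongside as supportive.
4. When a benchmark is chosen, compare like with like: confirmed with confirmed, or unconfirmed with unconfirmed.
5. Date DOR from the first of the two scans, and state that confirmed responders then have a DOR of at least about 8 weeks by construction.

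**Cost.** The change is one of wording. Patients still on schedule need no added imaging, because the next scan is already due about 56 days later. ORR will be lower. Patients who stop early may be impossible to confirm, since EOT imaging can be skipped when a scan from the past month exists, so some true responses will be counted as non-responses. The supportive unconfirmed rate shows how many patients the two definitions separate.

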Procedures	G		Cycle 1 ¹¹			≥ Cycle 2 ¹¹			
Study Day	Screening Days –30 to 1	Day 1	Day 8	Day15	Day 1	Day 15	End of Even Cycles	EOT ¹¹	EOS ¹²
Informed Consent	Х								
Inclusion/Exclusion Criteria	Х								
Medical history ¹	Х								
Concomitant medications	Х	X ¹³	X	Х	Х	Х		Х	
Demographic data	Х								
Height	Х								
Vital signs, weight	Х	X ¹³	X	Х	Х	X		Х	
Physical examination ²	Х							Х	
Neurologic examination	X	X ¹³	X	Х	Х	Х		Х	
ECOG Performance Status	X	X ¹³	X	Х	Х	Х		Х	
ECG ³	X	Х	X	Х				Х	
Hematology ⁴	X		X	Х	Х	Х		Х	
Coagulation ⁴	Х								
Chemistry ⁴	X		Х	Х	Х	Х		Х	
Urinalysis ⁴	Х								
Pregnancy test ⁵	X							Х	
Disease assessment using RECIST ⁶	X						Х	Х	
Drug administration ⁷		Х	X ¹⁴	X ¹⁴	Х	Х			
Patient Observation ⁸		Х	Х	Х	Х	Х			
Hospital admission ⁹		Х							
Assessment for AEs ¹⁰		Х	Х	Х	Х	Х		Х	Х

AE: adverse event; ECG: electrocardiogram; ECOG: Eastern Cooperative Oncology Group; EOS: end of study; EOT: end of treatment; RECIST: response evaluation criteria in solid tumors.

¹ Full medical history at screening.

² Full physical examinations will be done at screening and EOT visit only; all other endpoints will employ assessment of AEs and captured in AE and disease assessment CRFs.

IMSA101 Clinical Study Protocol: IMSA101-101

the assessment is indicated.

3

- ⁴ Laboratory analyses will be performed by local lab and include hematology, coagulation, chemistry, and urinalysis. Screening labs must be performed \leq 72 hours prior to Cycle 1, Day 1. Refer to Section 6.6 for details.
- ⁵ If the patient is a woman of childbearing potential, a serum pregnancy test must be performed during screening and at EOT.
- ⁶ Disease assessments will include radiographic assessments and if applicable, photographic assessments of skin lesions, prior to the end (≤ 7 days) of every even numbered treatment cycle (Cycle 2, Cycle 4, etc.), and EOT. Photographic assessments of skin lesions will be performed through a photography vendor at the same time points as the radiographic assessments. Detailed instructions for photography will be included in a separate photography manual. In certain circumstances a patient experiencing RECIST progression of disease may be allowed to continue therapy on study where there is agreement between the investigator and sponsor that the patient is deriving clinical benefit.

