3 STUDY DESIGN

3.1 STUDY DESIGN OVERVIEW

This is an open-label, dose escalation (Phase I), and dose expansion (Phase IIA) study designed to evaluate safety and efficacy of IMSA101 alone or in combination with an ICI (Phase I and II). Therefore, the study will be conducted in 2 phases. The dose of IMSA101 in Phase IIA will be based on the monotherapy and combination RP2Ds from Phase I.

The following methodology applies to all patients (unless otherwise indicated):

- Pre-treatment screening radiographic tumor assessments will be collected within 30 days prior to initial dose for all patients. Photographic assessments of skin lesions will be performed as detailed in a separate photography manual.
- Treatment cycles will be 28 days in duration with lesions injected weekly on Day 1 for the first three weeks of Cycle 1 and then every 2 weeks during Cycles 2 and beyond.
- A single pre-defined lesion/lesion site (longest diameter ≥ 10 mm and ≤ 50 mm) shall be injected throughout study duration, if possible. Where the original injection site is considered by the investigator to become inaccessible, a second lesion/lesion site shall be selected as a replacement and this shall be used henceforth so long as it is considered accessible. Subsequent injection sites shall be replaced when they are considered inaccessible.
- Where no remaining accessible lesions are present and where benefit of IMSA101 therapy is, in the opinion of the investigator, being derived by the patient, continued injections of IMSA101 into the vicinity of an inaccessible lesion or, in the case that a lesion can no longer be radiographically visualized, into the last known location of the non-visible lesion shall be allowed.
- Patients will be admitted to the hospital for observation overnight following intratumoral injection with IMSA101 on Day 1 of Cycle 1. Patients will be followed throughout the study for drug tolerability and safety by collection of clinical and laboratory data, including information on adverse events (AEs) using CTCAE v5.0 criteria, serious AEs (SAEs), DLTs, concomitant medications, vital signs, and ECGs.
- Patients will be assessed for anti-tumor efficacy based on radiographic assessments and if applicable, photographic tumor assessments, and analysis of ORR, DOR, TTP, and PFS using RECIST v1.1 criteria (Appendix 13.2) at screening and the end (≤ 7 days) of even numbered cycles (Cycle 2, Cycle 4, etc.) after the first dosing.

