5.1.9 End of Study Visit (Safety Follow-up 30 days after Last Dose)

• Assess and record AEs.

5.1.10 **Cycle Extensions**

During this study, with the approval of the investigator and sponsor, a patient may be allowed a 2 week delay or extension between cycles. Rationale for delay or extension should be documented.

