10.3.6 Adverse Events

- AEs will be coded using the Medical Dictionary for Regulatory Activities (MedDRA) coding dictionary. A listing of all events, with seriousness, severity, relationship, sequelae, and beginning and end times will be provided.
- Narratives for any SAEs will be provided.
- Deaths, SAEs, and AEs leading to discontinuation of trial medication will be summarized by primary system organ class and preferred terms.
- Listings will be provided.

10.3.7 **Tumor Assessments**

All known sites of disease must be documented at screening and re-assessed at each subsequent tumor evaluation according to procedures described in Section 6.9.

Patients will be assessed for anti-tumor efficacy using RECIST v1.1 criteria (Appendix 13.2) at the end (\leq 7 days) of every even numbered cycle (Cycle 2, Cycle 4, etc.) after the first dosing.

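### Appendix 13.2, as printed, leaves the pre-treatment baseline out of the reference for target-lesion progression

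*Combined protocol and SAP*

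**What the plan says.** Appendix 13.2 requires, for PD by measured lesions, a rise of at least 20% and at least 5 mm over the "smallest sum of diameters recorded since the treatment started". The baseline scan comes earlier. Section 3.1 says: "Pre-treatment screening radiographic tumor assessments will be collected within 30 days prior to initial dose for all patients".

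The same appendix treats its other categories as follows:

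- **Partial response** requires a fall of at least 30%, "taking as reference the baseline sum LD".
- **Stable disease** is described as a steady state, followed by: "Neither sufficient shrinkage to qualify for PR nor sufficient increase to qualify for PD".
- **Response Duration and Stable Disease Duration** both run to progression, "taking as reference the smallest measurements recorded since the treatment started".

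Appendix 13.2 says that findings are assessed by RECIST v1.1. It also says that each patient's best response is classified by the definitions it then prints. Disease assessments fall at the end "of every even numbered treatment cycle (Cycle 2, Cycle 4, etc.), and EOT" (Table 2, footnote 6). Section 2.4.3 lists time to progression (TTP) and progression-free survival (PFS) among the secondary efficacy endpoints.

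**The concern.** A sum measured before the first dose has not been recorded since treatment started. The appendix names baseline where it wants baseline, under partial response, and does not name it for PD. No other section says that the baseline sum counts towards the smallest sum.

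Read literally, the rule has no reference value at the first on-treatment scan. That scan can only set the reference for later ones. A tumour that has already grown by more than 20% then raises the bar for its own progression.

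The PD date feeds TTP, PFS and stable-disease duration, and the PD call feeds best response. The study is open-label and non-randomized (Section 3.4). Section 10.1.1 leaves to the final SAP the criteria for telling the drug apart from standard-of-care benchmarks. With no concurrent control, a progression rule that runs late would flatter any such comparison.

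**Working it through.** The plan gives no figure on this point, so there is none to reproduce. The check applies the printed rule to example sums under two readings of the reference.

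**Inputs from the documents**
- PD threshold: at least +20% and at least +5 mm over the reference (Appendix 13.2).
- Cycle length: 28 days (Section 10.2.2).
- Scans at the end of even-numbered cycles, so the nominal interval is 2 × 28 = 56 days, or 8 weeks.

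**Assumed inputs:** a baseline target sum of 40 mm, and the growth patterns below.

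**Formula.** PD occurs at the first scan where the sum is at least max(1.2 × R, R + 5 mm). R is the smallest earlier sum, either with baseline included or from on-treatment scans only. For any R of 25 mm or more, 20% of R is at least 5 mm, so the 5 mm condition does not bind here.

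**Steady growth from 40 mm.** With baseline included, R = 40 and the threshold is 1.2 × 40 = 48 mm. As printed, R is the first on-treatment sum.

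| Growth per 8 weeks | Sums at weeks 8, 16, 24 (mm) | PD, baseline included | Threshold as printed (mm) | PD as printed |
|---|---|---|---|---|
| 10% | 44.0, 48.4, 53.2 | week 16 | 1.2 × 44 = 52.8 | week 24 |
| 15% | 46.0, 52.9, 60.8 | week 16 | 1.2 × 46 = 55.2 | week 24 |
| 20% | 48.0, 57.6, – | week 8 | 1.2 × 48 = 57.6 | week 16 |
| 30% | 52.0, 67.6, – | week 8 | 1.2 × 52 = 62.4 | week 16 |
| 50% | 60.0, 90.0, – | week 8 | 1.2 × 60 = 72.0 | week 16 |

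The delay is one scan, 8 weeks, in every row. At 20% growth the tumour is 57.6/40 = 1.44 times baseline when PD is first recorded. At 10% it is 53.2/40 = 1.33 times baseline.

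**Growth, then plateau**
- 40/50/50/50 mm: with baseline, week 8 is +10 mm and +25%, so PD. As printed, R = 50 and PD needs 60 mm, which is never reached.
- 40/48/48/48 mm: with baseline, PD at week 8 (+8 mm, +20%). As printed, PD needs 57.6 mm, which is never reached.

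**Sum falls below baseline first**
- 50/46/50/58 mm: R = 46 under both readings, the threshold is 55.2 mm, and PD is at the third on-treatment scan either way.
- 50/30/33/40 mm: R = 30, the threshold is 36 mm, and PD is again at the third on-treatment scan either way.

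**Duration definitions.** A partial responder's sum is at most 0.70 × baseline, so baseline is never the smallest value and Response Duration does not change. Stable Disease Duration does change in patients whose sum only rises.

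**The case against.** The strongest reply is that nobody would apply the rule this way. RECIST v1.1 is named as the standard in Sections 3.1, 6.9 and 10.3.7 and at the head of Appendix 13.2. Section 6.9 has all disease sites documented at screening and re-assessed. The appendix asks for one measurement method at baseline and follow-up, and counts stable disease from the start of therapy. All of this presupposes a pre-treatment comparator, and a PD rule without a reference at the first scan is unworkable. This makes harm unlikely, and it is why the point is minor. It does not correct the text, because the appendix makes its own printed definitions the basis for classifying patients.

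A reader might infer that growth at the first scan would definitely be recorded as stable disease. The documents do not go that far. Stable disease is defined partly as neither response nor progression, which points that way, but also as a steady state, which a rise from 40 to 50 mm is not. The literal result is stable disease or undefined.

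A reader might also infer that median TTP or PFS would be overstated by 8 weeks. That is not supported either. The 8 weeks is a per-patient figure under assumed growth patterns. The documents give no proportion of patients who would progress by target-sum growth alone, without new lesions, non-target progression or earlier shrinkage.

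Finally, Section 2.4.3 says only that the secondary efficacy endpoints may include TTP and PFS, and Section 10.1.1 calls the Phase IIA statistics mainly descriptive. Both limit the consequence.

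**Conclusion.** The printed PD reference is wrong as written, and no other section repairs it. Under literal application, target-lesion PD cannot be called at the first on-treatment scan. In patients whose sum never falls below baseline it is recorded one scan late (8 weeks in the steady-growth examples) or missed (the plateau examples). These sizes rest on the assumed 40 mm baseline, the assumed growth patterns and the nominal 8-week interval.

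The effect is confined to TTP, PFS, best response and stable-disease duration. It does not reach PD by new or non-target lesions, patients whose sum first falls below baseline, ORR, or the primary endpoint (MTD/RP2D). Severity is minor, because assessors will probably follow the cited RECIST v1.1 guideline.

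**What to change.** In Appendix 13.2, under Progressive Disease, change the reference to *the smallest sum of diameters on study, including baseline*. Use the same wording under Stable Disease Duration, where it changes the result for tumours that only grow. Use it also under Response Duration, for consistency only.

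The cost is one phrase in three places of one appendix, with no added scans or data.
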